### *Adverse Event Reporting*

Unanticipated (unexpected) problems/events, those that are not already described as potential risks in the consent form, or not part of an underlying disease, will be reported to the IRB as soon as possible. The same will be done for serious problems/events and, in the opinion of the investigator, are possibly, probably or definitely related to the research procedures. A follow-up report will also be submitted to the IRB with any documentation related to a previously submitted adverse event.

### *Risks*

Participants may experience side effects while taking the drugs used in this study. Side effects are usually reversible when the drug is stopped but occasionally continue and may cause serious complications, if subjects experience any side effects, they will be asked to contact the study doctor immediately.

There may be other risks that could arise which are not reasonably foreseeable. If new information becomes available which could influence their willingness to continue, this new information will be discussed with the participant.

While taking the study drug, the subject's condition may remain the same or worsen due to no effect of the study drug.

### *Risks of Brexpiprazole*

The most common side effects associated with Brexpiprazole include:

- Weight gain
- Inner sense of restlessness (feeling like one needs to move)

Brexpiprazole may cause more serious side effects including:

- Stroke in elderly people
- Neuroleptic Malignant Syndrome (high fever, stiff muscles, sweating, changes in pulse, heart rate and blood pressure)
- Tardive dyskinesia (uncontrollable body movements)
- High blood sugar
- Low white blood cell count
- Decreased blood pressure
- Seizures
- Problems controlling your body temperature so that the individual feel too warm
- Difficulty swallowing that can cause food or liquid to get into the lungs

#### *Risks of Electrocardiogram*

If subjects are asked to get an ECG, they may have some discomfort when the electrodes (soft patches attached using adhesive tape) are removed from their chest and limbs. There is a possibility they could develop a minor rash when the electrodes were placed. This rash should go away without treatment.

#### *Risks of blood draws*

Needle sticks can cause discomfort, pain, burning sensation or bruising.

### **Data and Safety Monitoring Plan**

1. Responsibility for Data and Safety Monitoring  
The PI will have overall responsibility for monitoring the integrity of study data and participant safety.
2. Procedures for Monitoring Participant Safety  
The PI will implement the following procedures to ensure data integrity and the safety of participants during the study.
  - A number of elements of the research plan are intended to minimize the risks of study participation. If subjects become actively suicidal with intent and plan to kill themselves, the PI will evaluate them and refer them for immediate non-study treatment. Any participant endorsing suicidal thoughts with intent and plan will be immediately evaluated by the PI and referred to a higher level of care if clinically indicated.
  - The PI will evaluate patient safety and resolve any safety issues if necessary, as such issues arise. The PI will also be responsible for preparing written summary reports of adverse events and will prepare a written report summarizing any decisions that are made pertaining to participant disposition.
  - Data integrity and confidentiality will be safeguarded as discussed above in the Data Management and Statistical Analysis section under Research Methods.

### **Monitoring Committee**

We will establish a monitoring committee and define in detail its role, its composition, and its operating procedures for reviewing patient safety and data from this study. The monitoring committee, comprised of two individuals independent of personnel involved in the study, including a psychiatrist and a statistician, will come together via conference call yearly. The committee will use a standardized approach employing contemporary bio statistical, psychiatric/psychological, and ethical principles to review study design and interim data every year. The committee will audit the records from the study and will ensure the data are being collected, managed and protected. The committee will have the ability to ask for more frequent

reviews at any time if they deem it necessary. In addition, the PI will inform the committee of any serious adverse event.

The PI will prepare a specific report for the committee in advance of each meeting. Attention will be given to data quality and timeliness, recruitment, risk versus benefit, adverse events and other factors that could affect study outcome.

### **3. Reporting Adverse Events**

- Any serious adverse event will be reported to the Institutional Review Board (IRB) at the University of Chicago in a full written report within 10 working days of the event. For fatal/life-threatening serious adverse events, the PI will notify the IRB Chair by phone immediately.
- Any moderate adverse event which appears definitely, probably, or possibly related to study participation will be reported to the University of Chicago IRB in writing within 20 working days.
- Any mild adverse event will be summarized in the IRB annual progress reports.

### **Data Analysis**

Data analysis will involve all visits during the 12-week double-blind treatment phase (up until week 12). Data from the tapering phase (weeks 12-13), although collected, will not be included for purposes of the primary goal of this study.

All enrolled subjects will be included in the analyses of baseline demographics and safety according to an intent-to-treat (ITT) principle. For statistical analysis, the full-analysis set will be defined as all participants who took at least 1 dose of the study drug and had at least 1 post-baseline primary efficacy assessment. The safety-analysis set will be defined as all randomized participants who took at least 1 dose of the study drug and completed at least 1 follow-up safety assessment.

The statistical model will be a linear mixed-effects regression model (LME) that includes terms for treatment group, time, and treatment-by-time interaction. The analyses will run using the nlme package on R for Windows (R Foundation, Vienna, Austria; <http://www.r-project.org>). Literature suggests LME without imputation may provide more accurate and stable results than LME models using fixed and multiple imputation methods for handling missing data, so no imputation will be undertaken for missing data. All tests of hypotheses will be performed using a two-sided significance level of 0.05.

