### **Randomization**

Participants are randomized (1:1) to receive placebo or brexpiprazole by the investigational pharmacy at the University of Chicago. The study blind will be maintained by over-encapsulation, making placebo and active treatments appear identical in size, weight, shape, and color. Dosage changes and reductions will not be permitted during the study and participants will be discontinued if they experienced intolerance.

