### **Efficacy evaluation:**

The primary outcome measure will be the change from baseline using the Zanarini Rating Scale for Borderline Personality Disorder (“Zanarini scale”) (45). This semistructured interview has anchored ratings (0=no symptoms, 4=severe symptoms) on nine items that correspond to the DSM-5 BPD criteria. Its subscales will be considered secondary efficacy measures.

Secondary efficacy measures include Modified Overt Aggression Scale (46), the Young Mania Rating Scale (47), and the self-report version of the Zanarini scale (48), the Borderline Evaluation of Severity Over Time (49), the Barratt Impulsiveness Scale (50) the Minnesota Impulsive Disorders Interview (51), the Symptom Checklist–90–Revised (SCL-90-R) (52), and the scales listed above (41-44).

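### The efficacy set drops randomised participants who have no post-baseline Zanarini rating, and no all-randomised or sensitivity analysis shows whether that matters

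*Combined protocol and SAP*

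**What the plan says.** The Data Analysis section defines the full-analysis set as participants who "took at least 1 dose of the study drug and had at least 1 post-baseline primary efficacy assessment". Its intent-to-treat sentence is narrower than a quick reading suggests: "All enrolled subjects will be included in the analyses of baseline demographics and safety according to an intent-to-treat (ITT) principle". Efficacy is not mentioned there.

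The model is "a linear mixed-effects regression model (LME) that includes terms for treatment group, time, and treatment-by-time interaction", and the section adds "so no imputation will be undertaken for missing data". No sensitivity analysis for missing data and no efficacy analysis of all randomised participants is described.

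Under Efficacy evaluation, "The primary outcome measure will be the change from baseline using the Zanarini Rating Scale for Borderline Personality Disorder". The plan does not say whether the model's response is the change score or the rating itself with baseline as the first value.

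Three other sections determine who might be lost early:
- **Randomization:** no dose change is allowed, and "participants will be discontinued if they experienced intolerance".
- **Study Design/Methodology:** visits are weekly at the start, so the first follow-up rating is due at week 1.
- **Subject Withdrawal:** a participant who withdraws repeats the screening instruments at a termination visit, if able to attend.

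**The concern.** Both conditions for entering the efficacy set, taking a dose and having a later rating, are met or missed after randomisation. If the reasons for missing them differ between arms, the groups compared are no longer those that randomisation produced. The rule on intolerance gives one route by which early loss could be tied to treatment. The dosing condition is the lesser worry while the blind holds; the rating condition is the one that treatment can plausibly affect.

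The restriction is also unnecessary for the chosen method. A likelihood-based mixed model uses whatever ratings exist. If baseline is one of the responses, a participant with only a baseline rating contributes to the fit. Dropping that participant discards information the model could use when loss depends on baseline severity. With 40 per arm, each excluded participant is 1/40 = 2.5% of an arm.

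**Working it through.** **Inputs from the documents.** 40 per arm, 1:1 allocation, two-sided 0.05, first follow-up at week 1, analysis through week 12. The Sample Size section states no effect size, standard deviation, power or dropout rate, so its 40 per group cannot be reproduced. By back-solving with the normal approximation, 40 per arm corresponds to a standardised effect of (1.960 + 0.842) × √(2/40) = 0.626 at 80% power. I use this only as a scale.

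**Step 1: excluded participants gain nothing from the drug.** Assume k of 40 are excluded on drug and none on placebo. The as-randomised effect is (1 − k/40) times the effect in those kept. Relative to the as-randomised effect, the kept effect is too large by (k/40)/(1 − k/40) = k/(40 − k).

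| k | k/(40 − k) | effect of 0.626 in those kept becomes, over all randomised |
|---|---|---|
| 2 | 2/38 = 5.3% | 0.626 × 38/40 = 0.595 |
| 3 | 3/37 = 8.1% | 0.626 × 37/40 = 0.579 |
| 4 | 4/36 = 11.1% | 0.626 × 36/40 = 0.563 |

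Under this scenario a true effect of zero produces no bias.

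**Step 2: no true effect, but the excluded would have done worse.** If those excluded from the drug arm would have ended δ SD worse, the bias towards the drug is δ × k/(40 − k). For δ = 0.5 to 1 this is 0.026 to 0.053 SD at k = 2 and 0.056 to 0.111 SD at k = 4.

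**Step 3: does keeping baseline-only participants help?** This was simulated with 1,500 trials per scenario, 40 per arm and ratings at weeks 0, 1, 2, 4, 6, 8, 10 and 12. The model had group, linear time and their interaction, with baseline as a response and known variance components. Assumed, not in the documents: mean baseline 18, intercept SD 4, slope SD 0.35 per week, intercept-slope correlation −0.2, residual SD 3, and about 10% of the drug arm (4 of 40 on average) lost before any post-baseline rating, with none lost on placebo. Results are mean week 12 estimates in points with no true effect; negative favours the drug.

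| reason for early loss | complete data | plan's set | all randomised |
|---|---|---|---|
| purely random | −0.03 | −0.02 | −0.02 |
| high baseline score | −0.01 | +0.14 | 0.00 |
| worse individual course (not at random) | −0.01 | −0.39 | −0.36 |

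The Monte Carlo standard error of each mean is about 0.03. The standard error of one trial's estimate is about 1.20, so the two biases are roughly 0.14/1.20 = 0.12 and 0.39/1.20 = one third of a standard error. Keeping everyone removes the bias when loss depends on baseline score. It removes only about 7% of the bias when loss is not at random (from unrounded values, 0.025 of 0.371). The shifts were similar with a true drug benefit of 0.2 × 12 = 2.4 points.

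**Step 4: choice of response.** If the response is change from baseline, a participant with no later rating has no response value. Widening the set would then change nothing. The gain in the second row depends on baseline being a response.

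**The case against.** The strongest reply is that few people can be affected. The first follow-up rating is at week 1, follow-up visits may be held online, and a withdrawing participant is asked to a termination visit. Entry requires a Zanarini score, so that visit should yield a rating. Someone stopped for intolerance who attends stays in the set. The Sample Size section expects few dropouts. All of this stands and limits the size of the problem. It does not remove it, because attendance at the termination visit is conditional and no dropout rate is given.

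A second reply is that a dosed-and-rated set is a prespecified, disclosed choice. That also stands. A reader might infer that the plan contradicts its own intent-to-treat statement, but that sentence covers baseline demographics and safety only, so there is no inconsistency to report.

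A reader might also infer that the exclusion favours the drug because early loss must be commoner on active treatment. The documents give no early-loss rate by arm, and the intolerance rule applies to both arms. In the simulation, loss driven by high baseline scores biased the plan's set against the drug. The direction is not established.

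Finally, widening the set does little for the one simulated mechanism that did favour the drug. That is correct, and it is why the fix cannot stop there.

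**Conclusion.** The point holds as a modest weakness in the choice of analysis set. The plan excludes randomised participants on post-randomisation events that may differ by arm, the model does not need it to, and nothing planned would reveal the consequence. The sign of any bias is unknown.

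The illustration of 5.3% to 11.1% rests on assumed counts of 2 to 4 exclusions, all on drug, with no drug benefit in those excluded. If early loss is rare or balanced the effect is negligible, and the documents suggest, without a rate, that it will be low. The simulated figures rest on assumed variances and a 10% drug-arm loss, and they show direction and relative size only. The loss of precision is small: at a standardised effect of 0.626, losing 4 from one arm lowers power from 79.9% to 77.8%.

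The documents do not support a claim that the result would be biased towards the drug or that the randomised comparison is necessarily broken.

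**What to change.** Before unblinding, amend the Data Analysis section as follows:

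1. Define the primary efficacy set as all randomised participants, analysed in the arm to which they were randomised.
2. State that the response is the Zanarini rating at every visit including baseline. The treatment-by-time term then gives the difference in change from baseline to week 12, so the primary outcome is unchanged.
3. Add one not-at-random sensitivity analysis, reference-based or delta-adjusted. Zero change for participants with no post-baseline rating can serve as a conservative bound, but it is not the same as no drug benefit: if placebo participants improve, zero change is worse than placebo. It is conservative only when such losses fall mainly on drug, so read it beside the counts by arm. Imputation used here need not alter the decision not to impute in the primary model.
4. Report by arm how many randomised participants were never dosed or never rated after baseline, with reasons.
5. Keep the present full-analysis set as a supportive analysis.

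The cost is plan wording, an extra model run and the sensitivity analysis, with no new data collection. The primary estimate may shift slightly in either direction.

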#### *Assessments at each visit*

Those subjects who appear appropriate for the study, based on telephone screening, will be invited for a baseline assessment. The duration of the baseline assessment will be approximately 90 minutes and will include the following: Informed consent, Demographic data, Concomitant medications (no psychotropic medications will be allowed), Family history data, Medical evaluation including physical examination, EKG, weight, and vital signs, Urine pregnancy test (for women of childbearing years) and urine drug screen, and a psychiatric evaluation (using the following measures: MINI International Neuropsychiatric Interview (40); Depressive symptoms will be rated with the 24-item Hamilton Depression Rating Scale (HAM-D) (41); Anxiety

symptoms will be assessed using the Hamilton Anxiety Rating Scale (HAM-A) (42); Psychosocial functioning will be evaluated using the patient-rated version of the Sheehan Disability Scale (SDS) (43); Quality of Life Inventory (QOLI) (44); The Cambridge-Chicago Compulsivity Trait Scale (CHI-T); and the Columbia Suicide Severity Rating Scale (C-SSRS)). During the consent process, individuals will be given time to review the consent form and given the opportunity to ask any questions that may arise before signing the informed consent form. Throughout the study, subjects will be asked questions about the study to ensure that they continue understanding study procedures. Blood samples will be collected at both baseline and last visits to measure blood sugar, glutathione, and cholesterol levels. All follow-up visits will include safety measures (adverse events, vital signs, C-SSRS), weight, BPD measures, and other psychiatric measures.

Due to the pandemic of COVID19, study participants can perform their baseline and follow-up visits online using encrypted Zoom instead of in person visits. All inventories will be assessed. Blood samples and urine toxicology, however, will be at the discretion of the study PI. In cases where they are considered medically necessary, the participant can have them drawn locally and submitted to the study team.

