### *Safety Assessments*

Safety and tolerability will be assessed using spontaneously reported adverse events data, C-SSRS, vital signs, and by evaluating premature termination. Safety assessments (sitting blood pressure, heart rate, adverse effects, and concomitant medications) will be documented at each visit. Subjects who are an immediate suicide risk will be removed from the study and appropriate clinical intervention (e.g. hospitalization) will be arranged. Study team members are mandated reporters and as such, will arrange for the subject to be taken to the emergency room if any intent to harm themselves is expressed. Urine pregnancy tests will be performed at the initial visit. Subjects who have a positive urine pregnancy test will be excluded from the study. Assessment of side effects will be done at each visit.

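### The Data Analysis section gives two incompatible safety populations without saying which governs, and the named one could drop a dosed participant whose adverse event is on record

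*Combined protocol and SAP*

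**What the plan says.** Two statements in the Data Analysis section bear on who is analysed for safety. The first is general: "All enrolled subjects will be included in the analyses of baseline demographics and safety according to an intent-to-treat (ITT) principle". It sets no condition on dosing or follow-up. The section then turns to named analysis sets. It opens with "For statistical analysis, the full-analysis set will be defined as all participants who took at least 1 dose of the study drug", adds a requirement for a post-baseline primary efficacy assessment, and then defines the safety-analysis set as randomized participants "who took at least 1 dose of the study drug and completed at least 1 follow-up safety assessment".

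Other sections describe how safety data arise:

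- **Safety Assessments:** "Safety and tolerability will be assessed using spontaneously reported adverse events data, C-SSRS, vital signs, and by evaluating premature termination". The same section has the routine assessments documented at visits.
- **Assessments at each visit:** "All follow-up visits will include safety measures (adverse events, vital signs, C-SSRS), weight, BPD measures, and other psychiatric measures".
- **Risks:** "if subjects experience any side effects, they will be asked to contact the study doctor immediately".
- **Reporting Adverse Events** (Data and Safety Monitoring Plan, item 3): serious events go to the IRB, as do moderate events at least possibly related to participation. For the rest, "Any mild adverse event will be summarized in the IRB annual progress reports". None of these rules depends on a follow-up assessment having been completed.

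**The concern.** Safety stands beside efficacy in the primary objective, so its denominator should be fixed in advance. Here it is not, and neither statement yields the set of all participants who took the drug.

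The named set also conditions on something that happens after randomization: completing a follow-up assessment. The Randomization section has participants discontinued for intolerance. Someone who stops early, reports the problem by telephone and does not return would be dosed, would have an event on record, and might still fail the condition. That event could appear in reports to the IRB but not in the trial's safety results. Because early loss of this kind may be related to treatment, it need not be balanced between arms. Premature termination, which the plan lists as a safety measure, would be understated if it were summarised on the named set; no text says which set it uses.

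**Working it through.** **Comparing the two statements**

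| Participant | All-enrolled statement | Named safety-analysis set |
|---|---|---|
| Enrolled, never randomized | in | out |
| Randomized, never dosed | in | out |
| Dosed, no completed follow-up safety assessment | in | out |
| Dosed, at least one completed follow-up safety assessment | in | in |

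Reading enrolled as randomized removes only the first row of disagreement; the dosing and follow-up conditions remain. The opening words of the full-analysis-set sentence do not rank the two safety statements. Even if those words are taken to introduce both definitions, the earlier sentence still assigns safety to all enrolled subjects.

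**Can a recorded event fall in the third row?** Yes, conditionally. Spontaneous reports are a source of safety data, and subjects are asked to contact the study doctor at once, so an event can be recorded outside a visit. Under Study Design/Methodology the first follow-up visit comes after about a week on study drug. Under Subject Withdrawal the early termination visit depends on the subject being able to come in. The plan does not define a follow-up safety assessment or say whether an off-visit report counts as one.

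**Size.** The plan gives no event rate and no figure for early loss, so the counts below are assumptions. Only the 40 per arm comes from the plan (Sample Size). Notation for one arm with 40 dosed:

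- m = participants with an event, taken as 4
- k = dosed participants with no follow-up assessment
- j = those among the k who had an event
- u = those among the j whose event was never reported

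Named set: (m − j)/(40 − k). All-dosed set: (m − u)/40.

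| Case | Named set | All-dosed set | All-dosed minus named |
|---|---|---|---|
| k = 0 | 4/40 = 10.0% | 4/40 = 10.0% | 0 |
| k = 1, event on record (j = 1, u = 0) | 3/39 = 7.7% | 4/40 = 10.0% | 2.3 points |
| k = 1, event never reported (j = 1, u = 1) | 3/39 = 7.7% | 3/40 = 7.5% | −0.2 points |
| k = 1, no event (j = 0) | 4/39 = 10.3% | 4/40 = 10.0% | −0.3 points |

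For scale, the standard error of a 4/40 rate is √(0.1 × 0.9/40) = 4.7 points, so the largest shift in the table is about half of one standard error. A more adverse assumption is three dosed participants with recorded events but no follow-up assessment, and four others with events. That gives 4/37 = 10.8% on the named set and 7/40 = 17.5% among all dosed. Nothing in the plan supports a count that high.

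The all-enrolled reading moves the other way. With 40 assigned to an arm, one never dosed and 4 with events, it gives 4/40 = 10.0% against 4/39 = 10.3% among the dosed.

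**The case against.** The best defence is that the first sentence states a principle and the later sentences give the operative definitions, so a set named for safety analysis is naturally the one used for safety. That is a reasonable guess at intent. It does not remove safety from the all-enrolled sentence, and it leads to the set with the follow-up condition.

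The second defence is that losing a recorded event needs several things together: the named set must govern, an off-visit report must not qualify, and the participant must never complete any follow-up assessment. A single completed assessment keeps a participant and all their events. The plan makes that easy: there is a week-1 visit, an early termination visit is planned, and "study participants can perform their baseline and follow-up visits online using encrypted Zoom instead of in person visits". The Sample Size section expects few drop-outs. Serious events reach the IRB and the monitoring committee whatever set is used. All of this stands. It limits the likely size and is why the loss is stated only as possible. It does not settle which population governs.

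Third, the all-dosed set is not neutral, because dosed participants whose event status is unknown count as event-free. That is correct, and it is the reason for reporting their number by arm. Whether events in the taper week belong in the safety analysis is a separate question about the time window; it does not depend on which set is chosen.

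**Conclusion.** The concern holds. That the two safety populations are incompatible and unranked follows directly from the text and rests on no assumption. That the named set could exclude a recorded event is conditional: it requires that this set be applied, that off-visit reports not count as follow-up safety assessments, and that at least one dosed participant with a recorded event complete no such assessment.

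The numerical effect is unknown and probably small: 2.3 points for one such participant under the assumed counts, and nothing if there are none. No choice of set recovers an event that was never reported. The efficacy analysis, significance level and sample size are untouched. The point should be fixed, because the denominator for part of the primary objective is otherwise left to the analyst.

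**What to change.** In the Data Analysis section:

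1. Define one safety set: all randomized participants who took at least one dose, with no follow-up requirement.
2. State that every recorded adverse event in that set counts, by whatever route it was reported.
3. Restrict the all-enrolled sentence to baseline demographics. If all randomized is preferred there, name that population instead.
4. Report disposition and premature termination on all randomized participants.
5. Report, by arm, how many dosed participants had no follow-up safety assessment, so that readers can see how many have unknown event status.

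The cost is two sentences of wording and one count by arm, with no new data. Reported rates may move slightly in either direction. The wording should be settled before unblinding, so that the denominator is chosen without knowledge of the results.
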